9. STATISTICAL CONSIDERATIONS

9.1 General Design Issues

The study is a decedent-cluster randomized field experiment; clusters of prescribers within each decedent were randomly allocated to either treatment or control. This design avoided treatment contamination—clinicians prescribing to the same patient were able to share information about the intervention without diluting its effect. If two or more decedents had the same prescriber, that prescriber was assigned to one and only one of those decedents by random draw. Two factors served as random strata: 1) whether the decedent received a prescription from a clinician with a single or multiple deaths, and 2) whether opioids only, opioids in combination with benzodiazepines, or benzodiazepines only were the cause of death. The first strata is designed to form equivalent groups on prescriber risk posture. The second strata equated preference for type of scheduled drug prescribed in practice. Strata were crossed to form $2 \times 3 = 6$ randomization groups.

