9.2 Sample Size and Randomization

We calculated the sample size needed to detect an effect of the letter intervention using standard formulas for power analysis in cluster randomized trials and the ‘clusterPower’ package in R statistical computing language.(19) For this calculation we used data on decedents and prescribers at the San Diego County Medical Examiner between January 1 and December 31, 2013 published in Lev et al. 2016.(20) We assume a two-tailed test with a 5% Type I error rate

and an 80% chance to detect an effect. Lev et al.(20) found mean of 4.5 prescribers for each decedent in San Diego County. Coefficient of variation was not reported by Lev et al. 2016. We assume it to be 1.22, which implies that 99% of decedents had 20 or fewer prescribers in the year before their death. We assume a 5% difference in means and a standard deviation of +140 daily MME within cluster. Most clinician clusters for process measures have intracluster correlations that fall between 0.05 and 0.15.(21) We assume a more conservative intracluster correlation of 0.2; in our design we randomized by decedent to reduce intracluster correlation. We utilized the Taylor method for calculating variance inflation due to unequal cluster sizes. Under these assumptions, we would need 65 decedents per study arm.

9.2.1 Treatment Assignment Procedures.

The study is a decedent-cluster randomized field experiment; clusters of prescribers within each decedent were randomly allocated to either treatment or control. This design avoided treatment contamination—clinicians prescribing to the same patient were able to share information about the intervention without diluting its effect. If two or more decedents had the same prescriber, that prescriber was assigned to one and only one of those decedents by random draw. Two factors serve as random strata: 1) whether the decedent received a prescription from a clinician with a single or multiple deaths, and 2) whether opioids only, opioids in combination with benzodiazepines, or benzodiazepines only were the cause of death. The first strata is designed to form equivalent groups on prescriber risk posture. The second strata equated preference for type of scheduled drug prescribed in practice. Strata were crossed to form $2 \times 3 = 6$ randomization groups.

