For randomization, six decedent lists were generated from the crossed strata levels. Using random.org's sequence generator, true random integer sequences derived from atmospheric noise determined decedent order in each list. For each ordered list, prescribers to decedents in the first half were those who received the intervention.

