9.4.2 Secondary outcomes

As secondary hypotheses, we evaluate if the intervention cohort had 1) fewer high-dose opioid prescriptions (≥ 50 or > 90 MME per day), or 2) fewer new patients who were started on opioids. High-dose prescriptions were evaluated using censored regression on percent of clinician fills on high-dose. Chance of a fill being a “new start” were evaluated using logistic regression. These analyses were also conducted within a difference-in-differences framework.

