9.5 Data Analyses

Descriptive and inferential statistics will be carried out in STATA (Version 14.0; Stata Corporation, College Station, TX). The *cmp* command in STATA will be used to compute a difference-in-differences estimator within a mixed-model censored linear regression.(17) The difference-in-differences estimator compares the average change over time in MME dispensed for prescribers in the intervention group, compared to the average change over time for prescribers in the control group. The natural log transformation of MME ensures normally distributed data. Censored regression has a continuous component and a discrete one. Natural log MME doses estimated over days where opioids were dispensed in the name of a prescriber represent the continuous part, and days with no opioids filled in that prescriber’s name represent the discrete part of the model. We denote estimation of the dependent variable as $\log(\overline{MME})^*$ to distinguish it from uncensored estimation. The analysis is represented by:

$$\log(\overline{MME})^*_{ijk} = \beta_1 x_{1ij} + \beta_2 x_{2ij} + \beta_3 x_{3ij} + \delta_{i(k)} \quad [1]$$

where β_1, β_2 and β_3 are fixed effects coefficients on time, x_1 , intervention, x_2 , and time by intervention interaction, x_3 , respectively. Alphabetic subscripts describe the i th prescriber, j th prescription filled and k th decedent, the nested random intercept $\delta_{i(k)}$ is normally distributed with mean zero and variance, $\sigma_{i(k)}^2$, for each i prescriber nested in (i.e., having prescribed to) decedent $k, i(k)$. With natural log transformed data, the value $100 \cdot [\exp\{\beta_3\} - 1]$ measures the percentage change in MME attributable to the intervention when data are uncensored.(18) However, when data are censored the coefficient β_3 must be adjusted to reflect the effect on the observed outcome. We will evaluate data 3 months pre-intervention and 3 months post-intervention, with

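### Decedents are randomised within six strata, but model [1] and its one-year extension carry no stratum or stratum-by-post term and give no reason (minor: precision and calibration, not bias)

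*Combined protocol and SAP*

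**What the plan says.** Section 9.1 describes the stratification: "Two factors served as random strata: 1) whether the decedent received a prescription from a clinician with a single or multiple deaths", and three types of drug cause of death. Crossing them gives 2 × 3 = 6 groups. The stated purpose is balance on prescriber risk posture and on drug type; of the latter it says "The second strata equated preference for type of scheduled drug prescribed in practice". A prescriber shared by several decedents has a rule: "that prescriber was assigned to one and only one of those decedents by random draw".

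Section 9.2.1 gives the allocation: "For each ordered list, prescribers to decedents in the first half were those who received the intervention".

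Section 9.5 writes out model [1]. Its three coefficients "are fixed effects coefficients on time", intervention and time-by-intervention. The only other term is "the nested random intercept" for prescriber within decedent. The one-year analysis adds one regressor for the 3-month effect. Sensitivity analysis on regression assumptions is promised in general terms, without mention of strata.

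For the secondary outcomes, section 9.4.2 says "High-dose prescriptions were evaluated using censored regression on percent of clinician fills on high-dose" and names logistic regression for new starts, both within a difference-in-differences framework. It writes no equation and names no covariates.

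**The concern.** A trial that randomises within strata is ordinarily analysed with those strata in the model, so that the standard error reflects the restricted allocation. Here the strata were chosen because they were thought to reflect prescribing behaviour, yet the primary model omits them without comment.

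Two features of this design keep the point alive despite the pre/post contrast. First, a difference-in-differences removes stable differences between strata but not different trends. Second, halving each list balances decedents, whereas the analysis runs on prescribers and their fills, and the planned cluster sizes are very uneven.

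At stake are a little precision, a reported SE that may be larger than it should be, and a choice about adjustment (which terms, which models, how sparse lists are merged) that is left open until the data are in.

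**Working it through.** **Inputs from the plan (sections 9.1, 9.2, 9.5).** Six lists, each halved; 65 decedents per arm, so 2 × 65 = 130; mean 4.5 prescribers per decedent; coefficient of variation of cluster size 1.22 ("We assume it to be 1.22, which implies that 99% of decedents had 20 or fewer prescribers"); ICC 0.2.

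The 65 itself cannot be reproduced. The Taylor inflation is 1 + ((1.22² + 1) × 4.5 − 1) × 0.2 = 3.04, but the 5% difference needs a baseline mean that is not given. That is a separate matter; 65 enters here only as the trial size.

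**Assumptions not in the plan.** f is the share of the variance of prescriber change explained by stratum, taken as 0 to 0.10. The ICC of change is 0.2 with f inside it; the plan gives 0.2 as a planning value, not for change. At f = 0.10, strata already account for half of all decedent-level variance in change. Stratum sizes were 22, 22, 22, 22, 22, 20 or 50, 34, 6, 22, 14, 4. Mean cluster size was 4.5, or 3.0 to allow for each shared prescriber counting once.

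**Step 1: what cancels.** Let stratum s have level a_s and trend b_s. On the change scale a_s drops out (approximately so in a censored model). The trends contribute Σ b_s (share of s in intervention − share of s in control). Because each list is halved at random, this averages to about zero, so there is no systematic bias. In a single randomisation it need not be zero. In a 22-decedent stratum the intervention share of prescribers has SD 0.12 and lies outside 40–60% in 41–44% of randomisations. In a 50-decedent stratum the figures are 0.08 and 22–25%.

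**Step 2: true SD of the effect, decedent clustering allowed for.** Simulated change scores, weight m/(1 + 0.2(m − 1)) for a decedent with m prescribers, across the assumed layouts and mean sizes:

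| f | Reduction in true SD from adding the terms |
|---|---|
| 0 | −0.6% to −0.3% (slightly worse) |
| 0.02 | −0.2% to 0.4% |
| 0.05 | 0.5% to 1.1% |
| 0.10 | 1.6% to 3.1% |

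**Step 3: reported SE.** For equal clusters of 4.5, the variance of a decedent's mean change is 0.2 + 0.8/4.5 = 0.378. The stratum share of it is R² = f/0.378, and adding the terms multiplies the reported SE by √(1 − R²).

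- f = 0.05: R² = 0.132, √0.868 = 0.931, a fall of 6.9%.
- f = 0.10: R² = 0.265, √0.735 = 0.857, a fall of 14.3%.

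Simulation with unequal clusters (mean 4.5) and cluster-robust SEs gave about 6% at f = 0.05 and 13.3–13.5% at f = 0.10. With mean 3.0 the falls were about 5% and 11%.

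**Step 4: calibration.** At f = 0.10 one run gave a true-SD reduction of 2.4% and a reported-SE reduction of 13.5%. If the adjusted SE is right, the unadjusted SE overstates its own SD by (1 − 0.024)/(1 − 0.135) = 1.128, or 13%. The null rejection rate is then 2[1 − Φ(1.96 × 1.128)] = 0.027. Simulation gave 0.028–0.029 without the terms and 0.048–0.052 with them.

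**Step 5: model [1] as written.** Its SE rests on a prescriber random intercept only. In a simulated censored model of that form (assumed variances, 30 days per period rather than three months), the mean reported SE went from 0.0258 to 0.0264–0.0265, a rise of about 2–3%, whatever f was. That SE would therefore not show any gain.

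**The case against.** The strongest reply is that the benefit is conjectural. No section says that trends differ by stratum, the stratification has a stated design purpose (balance) that is met without adjustment, and stable differences largely cancel. With clustering handled, the gain in true SD is at most about 3% for f up to 0.10. All of this stands, and it is why the point is minor. What remains is that the reported SE, once it allows for decedent clustering, is too large if strata do predict change.

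A second reply is that inserting the terms into model [1] alone achieves little, because its printed SE rises slightly. This also stands, so the fix must be tied to a suitable SE. Stratum terms do not repair the random-intercept-only SE, which is a separate issue.

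Three stronger readings are tempting and are not supported:

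- **Bias or inflated type I error from the omission.** Randomisation within lists protects the interaction coefficient. With a valid SE, the omission makes the test conservative.
- **Large precision gains.** Reductions in true SD of 8–36% can be produced, but only with weighting that ignores decedent-level clustering of change, unequal cluster sizes, and values of f absent from the documents. With equal cluster sizes the true SD did not change.
- **Strata omitted from the secondary models.** No equation is written for them, so the terms are unspecified, not shown to be absent.

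**Conclusion.** The point holds in a modest form. The primary model and its one-year extension leave out the factors by which the trial randomises, and the plan gives no reason. The consequence is some loss of precision and a conservative test under a clustering-robust SE, not bias.

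For f from 0 to 0.10 and an ICC of change of 0.2, the true SD changes by 0.6% worse to 3% better. With mean cluster size 4.5, the reported SE falls by about 6–7% at f = 0.05 and 13% at f = 0.10. If strata do not predict change, there is no gain. Every figure depends on f, on an ICC borrowed from the sample-size section, and on simulated change scores, not the full censored model. Severity: minor.

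**What to change.** In section 9.5:

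- Add the six-level randomisation stratum and its interaction with each post-period term to model [1] and the one-year model, used with an SE that allows for clustering of change by decedent. The interaction is the term that matters; a main effect alone adds little.
- Give each shared prescriber the stratum of the one decedent assigned under section 9.1.
- State in advance how sparse strata are merged, for example by pooling the single- and multiple-death levels within a cause-of-death type below a stated number of decedents per arm.
- If the terms stay out of the primary model, give the reason and name the stratum-adjusted model among the sensitivity analyses already promised.
- State whether the two secondary models carry the same terms. In the logistic model the odds ratio then becomes conditional on stratum. Under assumed new-start rates of 0.1 to 0.4, a conditional 0.80 corresponds to 0.80–0.81 without the terms if the stratum log-odds SD is 0.2–0.5, and to 0.82–0.83 if it is 1.0.

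Cost: SAP wording only, since every decedent already has a stratum. The 3-month model gains 5 + 5 = 10 parameters, and the one-year model 5 + 5 + 5 = 15 if it has two post-period terms. If strata do not predict change, about 0–3% of precision is lost.

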We will conduct a cluster randomized trial of an informative intervention targeting the over-prescription of scheduled drugs with patient death as the unit of randomization.

The follow outcomes will be analyzed:

- 1) Fewer opioid prescriptions written among clinicians receiving the letter, compared to controls;
- 2) Lower cumulative Morphine Equivalent Dose (cMED) among clinicians receiving the letter (as indicated by dosing on prescriptions filled);
- 3) More frequent use of CURES among clinicians receiving a letter;
- 4) Fewer opioid prescriptions for ≥ 100 milligram morphine equivalent (MME)
- 5) Fewer benzodiazepine co-prescriptions

In the main analysis, we will compare a 12-month baseline period to a 12-month post-treatment follow-up period.

Interventions and Duration

The intervention will be a one-time treatment for all participants, with a three-month and a one year follow-up period to measure the persistence of the effects after the intervention.

The following intervention will be analyzed:

A courtesy communication informing prescribers of the death of a former patient where prescription drug overdose was the primary cause or contributed to the cause of the death. The letter will invite prescribers to review materials regarding the clinical guidelines from the Center of Disease Control, the California Department of Public Health, and the San Diego County Prescription Drug Abuse Medical Task Force for a more prudent prescription of those drugs.

Sample Size and Population

Our sample will consist of a heterogeneous group of clinicians and allied health professionals with scheduled drug prescribing privileges practicing in San Diego County who prescribed a Schedule II-IV drug (i.e., drugs as defined by the United States Controlled Substances Act as having an abuse potential, but also a currently accepted medical use) to a person who died as a result of a Schedule II-IV accidental drug death.

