post-intervention beginning one month after the letter was sent to washout contamination by prescriptions written before receipt of the letter but filled afterwards. For the one-year analysis we will include a regressor to control for the 3-month effect. We will perform sensitivity analysis on regression assumptions. As secondary hypotheses, we evaluate if the intervention cohort had 1) fewer high-dose opioid prescriptions (≥ 50 or > 90 MME per day), or 2) fewer new patients who were started on opioids. High-dose prescriptions will be evaluated using censored regression on percent of clinician fills on high-dose. Chance of a fill being a “new start” will be evaluated using logistic regression. These analyses will also be conducted within a difference-in-differences framework.

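### The primary model has only a random intercept and no clustered variance is named, so the standard error of the treatment effect ignores how prescribers and randomised decedents differ in change

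*Combined protocol and SAP*

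**What the plan says.** The précis (Design and Outcomes) describes a cluster randomised trial "with patient death as the unit of randomization". Section 9.1 agrees: "clusters of prescribers within each decedent were randomly allocated to either treatment or control".

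For the primary analysis, Section 9.5 says the *cmp* "command in STATA will be used to compute a difference-in-differences estimator within a mixed-model censored linear regression". Equation [1] has fixed effects for time, intervention and their interaction (β3, the treatment effect). It has one random term, introduced with the words "prescription filled and k th decedent, the nested random intercept": a normal intercept for each prescriber nested in decedent. Observations are prescriber-days over 3 months before and 3 months after the letter, and days without a fill are treated as censored.

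No section names a random coefficient on time, a decedent-by-period term, or a robust, clustered or bootstrap variance. The nearest statement is "We will perform sensitivity analysis on regression assumptions", which does not mention clustering. For the secondary outcomes, Section 9.4.2 says only "These analyses were also conducted within a difference-in-differences framework".

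Section 9.2 sets the error rate: "We assume a two-tailed test with a 5% Type I error rate". It also inflates the sample size for decedent clusters: "We assume a more conservative intracluster correlation of 0.2".

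**The concern.** β3 compares changes. Each prescriber's random intercept appears in both the pre and the post period and is subtracted out. It protects a comparison of levels between arms but adds almost nothing to the variance of β3. A second intercept for decedent would cancel in the same way.

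What remains in the model-based variance is day-to-day residual noise, so every day counts as independent evidence about the effect of the letter. In reality some prescribers will cut back and others will not, for reasons unrelated to the letter, and prescribers to the same decedent may move together. That variation in change belongs in the standard error, at the level that was randomised. If it is left out, the primary p-value is too small and the confidence interval too narrow, and the error runs towards false positives.

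**Working it through.** **The plan's own figure.** The plan gives no standard error for β3, so there is none to reproduce. The 65 decedents per arm in Section 9.2 cannot be reproduced either, because the mean to which the 5% difference applies is not stated. It is used here only as the number of clusters.

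**Inputs from Section 9.2.** 65 decedents per arm; mean m = 4.5 prescribers per decedent; coefficient of variation CV = 1.22. This gives 65 × 4.5 ≈ 292 prescribers per arm. From Section 9.5: 3 months per period, so T ≈ 90 days.

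**Assumed inputs, not in the documents.** Daily residual SD on the log scale s = 1; SD of change between prescribers τ = 0.1, 0.2 or 0.3; share ρ of the change variance common to prescribers of one decedent = 0 or 0.2. A smaller number of informative days, T = 30, is also shown.

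**Linear formula, variance per prescriber change.**

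- Under equation [1]: 2s²/T. The intercept variance does not appear.
- True: 2s²/T + τ²(1 − ρ) + ρτ²·m(1 + CV²), where m(1 + CV²) = 4.5 × (1 + 1.4884) = 11.20.
- Type I error = 2[1 − Φ(1.96 / R)], where R is the true SE divided by the model SE.

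Example with T = 90, τ = 0.2:

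- Model variance: 2/90 = 0.0222.
- ρ = 0: true variance 0.0222 + 0.04 = 0.0622; R = √(0.0622/0.0222) = 1.67; Type I error 24%.
- ρ = 0.2: true variance 0.0222 + 0.04 × (0.8 + 0.2 × 11.20) = 0.0222 + 0.04 × 3.04 = 0.1438; R = 2.54; Type I error 44%.

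| T | ρ | R at τ = 0.1 / 0.2 / 0.3 | Type I error |
|---|---|---|---|
| 90 | 0 | 1.20 / 1.67 / 2.25 | 10% / 24% / 38% |
| 90 | 0.2 | 1.54 / 2.54 / 3.65 | 20% / 44% / 59% |
| 30 | 0 | 1.07 / 1.26 / 1.53 | 7% / 12% / 20% |
| 30 | 0.2 | 1.21 / 1.68 / 2.26 | 10% / 24% / 39% |

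At τ = 0, R = 1 and Type I error is 5%.

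**Does it carry over to the censored model?** A random-intercept censored regression was simulated with β3 = 0, intercept SD 1, s = 1 and T = 90. There were 1,000 replicates at 50% censoring and 500 at 80%; the Monte Carlo SE is at most 1.6 and 2.2 points respectively. Rejection rates with model standard errors:

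| Censored days | τ = 0 | ρ = 0, τ = 0.1 / 0.2 / 0.3 | ρ = 0.2, τ = 0.1 / 0.2 / 0.3 |
|---|---|---|---|
| 50% | 4% | 10% / 21% / 33% | 16% / 36% / 50% |
| 80% | 5% | 8% / 17% / 28% | 13% / 28% / 42% |

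Standard errors clustered on decedent gave 4.2% to 7.0% across all 14 settings.

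**Does the level of clustering matter?** A linear simulation (1,500 runs, same cluster sizes, T = 90) used prescriber change SDs of 0.1, 0.2 and 0.3 with additional decedent change SDs of 0.05, 0.10 and 0.15. Rejection rates were:

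- random intercept only: 24%, 47%, 61%;
- clustering on prescriber: 15%, 21%, 23%;
- clustering on decedent: 7.3%, 6.2%, 6.5%.

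Clustering on prescriber is not enough if decedents differ in change.

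**The case against.** **The plan is silent rather than wrong.** It never says that default model-based standard errors will be used, and equation [1] is shorthand: it prints no residual term. A clustered variance may be used in practice. That is possible, but the text describes a single random intercept and nothing else, and a plan should fix the variance method of its primary test in advance. The consequence is conditional on the model being fitted as written.

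**The size rests on assumptions.** This stands. τ, s and ρ are not in the documents, and the inflation depends on τ relative to s. With s = 2 and T = 90, the same formula gives 6%, 10% and 17% at ρ = 0, and 9%, 20% and 33% at ρ = 0.2. At s = 1, τ = 0.05 and ρ = 0 it gives 6%. The range runs from negligible to severe. As a guide to scale only, Section 7.1 watches for reductions of more than 20%, and ln 0.8 = −0.22 is of the same order as the assumed change SDs.

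**The correlation in Section 9.2 concerns levels, not change.** This is a fair reading, and using 0.2 as the share of change variance is an assumption. Even so, the sample size allows for correlation within decedent, while equation [1] has no component common to prescribers of the same decedent.

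**Clustered errors are not exact.** They reached 7.0% in the censored simulations and 7.3% in the linear one. They are still far closer to 5% than the model-based errors when change varies.

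**Conclusion.** The concern holds. As Section 9.5 is written, the standard error of β3 contains no variation in change between prescribers or between the decedents who were randomised. Unless all prescribers within an arm change by the same amount, it is too small and the 5% error rate in Section 9.2 is not kept. The mechanism and the direction do not depend on the assumed values; the size does. The percentages above illustrate it and are not predictions for this trial. Because this affects the primary p-value and confidence interval, it must be fixed. A sensitivity analysis would not repair the primary result. For the secondary models, the finding is that no variance method is stated.

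**What to change.** In Section 9.5, state that the variance of β3 is computed with cluster-robust standard errors at decedent level, and say the same for the secondary difference-in-differences models in Sections 9.4.2 and 9.5. At 65 decedents per arm there would be about 130 clusters. The cost is one sentence and one variance option; the estimator is unchanged and the confidence intervals become wider. Random effects of time at both prescriber and decedent level are an alternative, but a larger change to the model.

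Two separate points, neither of which causes the inflation:

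- Include the six randomisation strata and their interaction with time, to match the design and gain precision.
- Reconcile Section 3, which names the prescriber as the unit of randomisation, with the précis and Section 9.1, which name the decedent, so that the clustering level is unambiguous.

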5.2 Handling of Study Interventions

Letters will be carefully edited by an advisory group to ensure tone is supportive and its recommendations consistent with CDC guidelines. Letters will be generated, signed by the San Diego Medical Examiner and posted in the U.S. mail. The pre-intervention baseline period will be 12 months in length with a one year follow-up period to measure the persistence of effects after the intervention.

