6.1.2 Enrollment, Baseline, and/or Randomization

Enrollment

Participants will not be enrolled; we will intervene on all clinicians and allied health professionals with prescribing privileges and at least one prescription drug death as part of a public health program to encourage safe prescribing in San Diego County. Informed consent of patients and clinicians is waived under HHS regulations at 45 CFR 46.116(c), as the study is evaluating a County public service safe prescribing program.

Baseline Assessments

For the baseline assessment, the study team will evaluate physician prescribing practices in the 12 months pre- intervention using data from the CURES database.

Randomization

For randomization, six decedent lists were generated from the crossed strata levels. Using random.org's sequence generator,(16) true random integer sequences derived from atmospheric noise determined decedent order in each list. For each ordered list, prescribers to decedents in the first half were those who received the intervention.

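### The 3-month log-MME analysis leaves nine of the twelve collected baseline months unused, without a stated reason; the cost is precision, and its size depends on correlations the plan does not give

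*Combined protocol and SAP*

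**What the plan says.** The Combined protocol and SAP plans a full year of pre-letter data. Section 5.2: "The pre-intervention baseline period will be 12 months in length with a one year follow-up period". Section 6.1.2: "the study team will evaluate physician prescribing practices in the 12 months pre- intervention using data from the CURES database".

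Section 9.5 displays one model, equation [1]: log MME on time, intervention and their interaction, with a random intercept for prescriber nested in decedent. It contains no baseline covariate and no window. The window follows in the text: "We will evaluate data 3 months pre-intervention and 3 months post-intervention, with". The sentence then sets the start of the later window and gives its purpose: "post-intervention beginning one month after the letter was sent to washout contamination by prescriptions written before receipt of the letter but filled afterwards". The washout is the only reason attached to a window, and it concerns the post side.

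Two other places bear on the window. Section 9.5 adds: "For the one-year analysis we will include a regressor to control for the 3-month effect". It does not state that analysis's pre-window. The Précis, under Design and Outcomes, says: "In the main analysis, we will compare a 12-month baseline period to a 12-month post-treatment follow-up period". Section 9.4.1 defines the primary outcome as a change in log MME and names no window.

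**The concern.** A difference-in-differences estimate subtracts a pre-period level from a post-period level, so noise in the pre-period level passes straight into the variance of β3. In the 3-month analysis, months −12 to −4 of the same outcome are on file for both arms but enter neither the pre-period nor a covariate. Estimating a 3-month effect requires a 3-month post window; it does not require an equally short pre window.

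At stake is the width of the interval for the early effect. The cohort is limited to prescribers linked to one year of deaths (section 4.3), so baseline data are a source of precision that needs no further recruitment.

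**Working it through.** **Plan's own figure.** The plan gives no variance by window. Its sample size (section 9.2: 65 decedents per arm, 80% power) uses no pre/post window and cannot be reproduced, because the mean to which the 5% difference applies is not stated. It neither supports nor contradicts this point.

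**Inputs.** From section 9.5: pre months −3 to −1, one washout month (0), post months 1 to 3, one random intercept per prescriber. From sections 5.2 and 6.1.2: months −12 to −1 are available. Assumed: equal monthly residual variance s² and a linear model, which is an approximation to the censored one.

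**Notation.** L = mean of months −3 to −1; E = mean of months −12 to −4; P = mean of months 1 to 3. D = P − L is the planned change; C = E − L is the candidate covariate.

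**Case 1: exchangeable months (the structure of equation [1]).** The random intercept cancels.

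- 3 v 3: Var(D) = s²(1/3 + 1/3) = 0.667 s².
- 12 v 3 pooled: s²(1/12 + 1/3) = 0.417 s².
- 3 v 3 with covariate C: Cov(D, C) = Var(L) = s²/3 and Var(C) = s²(1/9 + 1/3) = 4s²/9. The reduction is Cov²/Var(C) = (1/9)/(4/9) s² = 0.25 s², leaving 0.667 − 0.25 = 0.417 s².
- Ratio: 0.417/0.667 = 0.625, a 37.5% cut (SE ratio √0.625 = 0.79). The slope on C is (1/3)/(4/9) = 0.75 = 9/12, so here the covariate form reproduces the 12-month mean exactly.

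**Case 2: true change varies between prescribers.** Add variance τs² to the change. The ratio is (0.417 + τ)/(0.667 + τ): 0.79 at τ = 0.5, 0.85 at τ = 1, 0.91 at τ = 2. These are cuts of 21%, 15% and 9%.

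**Case 3: serial correlation.** With AR(1) months at monthly correlation ρ, the covariate ratio is 1 − Cov(D,C)²/[Var(D)·Var(C)]. Variance ratios to 3 v 3:

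| ρ | Pooled 12 v 3 | 3 v 3 with covariate |
|---|---|---|
| 0.3 | 0.67 | 0.67 |
| 0.5 | 0.75 | 0.73 |
| 0.7 | 0.94 | 0.85 |
| 0.8 | 1.13 | 0.92 |
| 0.9 | 1.44 | 0.99 |
| 0.98 | 1.83 | 0.995 |

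Adding independent monthly noise of 0.5 to 2 times the AR(1) variance, at ρ of 0.8 to 0.98, gives 0.71 to 0.92 for the covariate form. In these cases the covariate form never raises the variance; pooling does when drift is strong.

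**Does the planned model report the gain?** Equation [1] is fitted to individual records, not period means. In simulations of a linear random-intercept version under Case 1, adding C and C × post cut the sampling variance of β3 by about 35–41%. The model-based variance fell by only 7% with one row per month and by 0–1% with 5 to 20 rows, because a prescriber-level covariate explains little of the row-level scatter. Cluster-robust variance did show the gain: ratio 0.62–0.63, or 0.78 with prescriber-by-period variance.

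**The case against.** **The main analysis may use all twelve months.** A reader might infer from section 9.5 that the trial's primary analysis discards nine months. The documents do not support that: the Précis states a 12 v 12 month main analysis, the one-year analysis has no stated pre-window, and neither section 9.4.1 nor equation [1] fixes one. What stands is narrower. A 3-month analysis is planned on either reading, and as written it uses three pre months. Settling which window is main would not bring the other nine into it.

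**A recent, symmetric window is defensible when prescribing drifts.** This holds against plain pooling, as Case 3 shows. It does not hold against the covariate form, which in the cases examined costs no precision. The plan does not offer drift as its reason.

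**The covariate alone would not narrow the reported interval.** This stands in full: without cluster-robust standard errors the fitted model largely hides the gain.

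**The covariate is not fully defined.** This also stands. The outcome is censored on days with no opioid fills, so the period means need a rule for such days and for empty windows. A new start needs a look-back that the documents do not define and that may reach before the 12-month extract.

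**Conclusion.** The point holds for the 3-month log-MME analysis only. Nine of twelve collected baseline months are unused there and no reason is given; separately, the 3-month window of section 9.5 and the 12-month window of the Précis are unreconciled.

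The avoidable variance is 37.5% if months are exchangeable around the prescriber's intercept, and about 0 to 33% under the serial correlation or prescriber-by-period variance examined. The plan gives neither quantity, so no single figure can be claimed. All figures are linear-model approximations.

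Two stronger readings should be avoided. First, bias: both windows precede the letter and allocation is randomised, so a short pre window costs precision only. Second, power: the exchangeable case would turn 80% into Φ(2.802/√0.625 − 1.960) = Φ(1.584) = 94%, but that is a best case from an assumed start. Section 9.2 did not compute its 80% for this model, with its windows, log scale and censoring.

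**What to change.** In section 9.5:

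1. State one main window, reconcile it with the Précis, and give the pre-window of the one-year analysis.
2. For the 3-month model, keep the 3-month post window, the washout and the difference-in-differences estimator. Add each prescriber's months −12 to −4 mean minus months −3 to −1 mean, as a main effect and multiplied by the post indicator.
3. State how days or whole windows with no fills enter those means.
4. Compute standard errors clustered on decedent.
5. Report the unadjusted 3 v 3 model as a sensitivity analysis.
6. Do the same in the high-dose model. Extend it to new starts only if the look-back that defines a new start lies within the extracted data.

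If the sponsor prefers 3 v 3 unadjusted, the plan should say why.

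The cost is a few sentences in section 9.5, one derived variable per outcome and two extra parameters per model. For log MME and high dose, the data are already in the 12-month baseline. The gain will be small if prescribing drifts strongly from month to month.
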